9 STATISTICAL ANALYSIS

9.1 SAMPLE SIZE DETERMINATION

We will enroll a total of at most 1800 patients. Sites are expected to enroll at least 1 or 2 patients per month.

Adaptive outcomes

The goal is to develop an adaptive clinical trial design which evaluates the therapeutic intervention of targeted therapy, identifies subset of subjects who respond better to the experimental therapy.

Sequential analyses will use the number of vasopressor-free days at day 28 as the measure of efficacy, and the occurrence of severe adverse events within the first 28 days as the measure of toxicity. According to the literature (the APPROCCHS trial), the number of vasopressor-free days at day 28 in the hydrocortisone+fludrocortisone group was 17.1 ± 10.8 versus 15.0 ± 11.1 in the placebo group. Thus, a sample of 176x2=352 patients achieves 80.04 % power to reject the null hypothesis of equal means when the mean difference between arms is 3 days with SD of 10 days, and with a significant level (alpha) of 0.05 using a two-sample t-test. For interactions to be detected with the same power as the overall effect, sample sizes should be inflated (Brookes 2004); estimated here at a multiple of fourfold; therefore, to handle potential dropouts, a sample of 1800 patients was considered to be enrolled.

Note that Bayesian inference will be used for sequential analyses, so that no inflation of type I error rate is to be corrected.

Primary outcome

To detect a 10% absolute risk reduction (from 45% to 35%) in the day 90 mortality, a sample size of 373 evaluable patients per arm (thus a total of 746 patients) is required to reach a 80% power. The planned sample of 1800 patients will achieve a 99.16%

power to reject the null hypothesis of equal mortality when the difference between arms is 10% overall, and with a 5% alpha level.

Sample sizes were computed using PASS 15 software (2017).

The power to detect this difference within each group of analysis will depend on the prevalence of each biomarker of interest.

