9.2 STATISTICAL METHODS

9.2.1 Adaptive Bayesian analyses

Clinical trial methodology needs to adapt to personalized medicine by including more frequent interim analyses of accumulating data, or by making greater use of those biomarkers information (Saad 2017; Janiaud 2019). An adaptive design is a clinical trial design that allows adaptations or modifications to aspects of the trial after its initiation without undermining the validity of the trial.

Therefore, the aim of the sequential analyses will be to detect treatment-by-biomarker interactions, that is, whether the treatment effect may be different according to biomarkers, that may potentially stop the recruitment of patients presenting with certain levels of that biomarker if there is any evidence that it interacts negatively with the outcome. Treatment effect will be assessed on two main outcome measures, namely a tolerance measure (to detect potential deleterious effects of treatment in some subsets) and an early surrogate efficacy measure (to detect a potential futility to continue treatment evaluation in some cohorts). As described above (section 4.8.2), the tolerance measure will be the occurrence within the first RECORDS" protocol, version 4.0 of 03/03/2021

7, 14 and 28 days of any grade 3 or over adverse events such as hospital-acquired infections, hyperglycemia, hypernatremia, neurological disorders, and the efficacy measure will be the number of vasopressor-free days within the first 28 days.

Search for treatment-by-cohort interactions will be based on each endpoint, and each cohort, separately. Let A and B denote the 2 treatment arms. The treatment effect, 0, of A over B will be considered as the parameter of interest.

Let consider a set of K biomarkers available at baseline, with $x_i = (x_{1i}, \dots, x_{Ki})$ the set of biomarkers for subject *i*, and $Y_{ii} = 1$ the outcome of subject i in arm j.

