We will use a Bayesian inference. This is in line with the growing literature to propose Bayesian approaches in randomized clinical trial (), including to identify subpopulations with enhanced treatment effects (Simon 2018). Moreover, it allows to go further than the "statistically significant" findings based on p-values (Wasserstein 2019; Amrhein 2019). Last, Unlike in the frequentist evaluation of the influence condition, the Bayesian evaluation of the influence condition has the advantage of separating the parameters of clinical relevance and risk tolerance (Millen 2014), as detailed below.

Search for treatment-by-cohort interactions will be based on each biomarker and outcome, separately. Treatment-by-covariate interaction will be measured by a Bayesian criterion proposed by Millen (2014), based on the posterior probability of the 'interaction condition' defined in terms of the subpopulation effect sizes estimates:

$P(\hat{\theta}_+/\hat{\theta}_- \geq \lambda_1 | X) \geq \gamma_1,$

where X is the observed data, $\hat{\theta}_+$ is the treatment effect on the efficacy outcome in one subset and $\hat{\theta}_-$ in the remaining subpopulation, λ_1 is a threshold of clinically meaningful effect, close to that proposed by Morita (2014), and γ_1 represents the information threshold for decision-making. Inversely, it will apply to the tolerance outcome, based on

 $P(\hat{t}_+/\hat{t}_- \ge \lambda_2 | X) \ge \gamma_2$, where \hat{t}_+ is the treatment effect on adverse event in one subset and \hat{t}_- in the remaining subpopulation, λ_2 is a threshold of clinically deleterious effect, and γ_2 represents the information threshold for decisionmaking.

The estimates $\hat{\theta}_i$ or $\hat{\tau}_i$ will be defined according to the type of the endpoint, either continuous, with $\hat{\theta}_j$ = $\frac{\hat{\mu}_{Aj} - \hat{\mu}_{Bj}}{\hat{\sigma}_{i}}$, is the effect size defined within each subgroup as the mean treatment

difference divided by the common standard deviation, or binary $\hat{\tau}_j = \frac{\hat{p}_{Aj} - \hat{p}_{Bj}}{|\bar{p}_j(1 - \bar{p}_j)|}$ where \bar{p}_j is the estimated

average adverse event rate.

Noninformative prior distribution will be considered.

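### The 80% power in section 9.1 belongs to a test on mean days, not to the ratio rule in section 9.2.1, and that rule's scaling can turn equal absolute effects into an apparent interaction

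*Protocol*

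**What the plan says.** **Sizing (Protocol 9.1, adaptive outcomes).** The protocol states that "a sample of 176x2=352 patients achieves 80.04 % power to reject the null hypothesis of equal means". The inputs are a gap of 3 days, an SD of 10 and alpha 0.05 in a t-test. On the search for interactions it adds: "For interactions to be detected with the same power as the overall effect, sample sizes should be inflated". The multiple is taken as four. That is 4 × 352 = 1408, and the total is raised to 1800 for dropout.

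**Decision (Protocol 9.2.1).** For the same sequential analyses, "the efficacy measure will be the number of vasopressor-free days within the first 28 days". An interaction is declared when P(θ₊/θ₋ ≥ λ₁ | X) ≥ γ₁, with a parallel rule for adverse events using λ₂ and γ₂. For a continuous endpoint, θ scales the gap in means between arms by a standard deviation that the text calls common. The definition opens with the words "is the effect size defined within each subgroup as the mean treatment". For a binary endpoint, the risk difference in subset j is divided by a term in p̄ⱼ(1 − p̄ⱼ), where p̄ⱼ carries the subset index. Priors are noninformative. The protocol gives no numbers for λ or γ.

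**The concern.** Two things do not fit together.

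First, the sizing argument concerns a difference in days, while the decision concerns a ratio of standardised effects. Power computed for the first does not carry over to the second. Section 9.1 nevertheless offers the fourfold step as preserving the power for interactions, and the ratio rule is how interactions will be judged.

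Second, if each subset's effect is divided by a quantity specific to that subset, the ratio mixes effect modification with differences in spread or background rate. Section 9.2.1 says that a negative interaction may stop recruitment at certain levels of a biomarker. Section 4.5.1 would use evidence of harm to mark a biomarker as identifying patients who should not receive the study drugs. A rule with unknown power, or one that responds to background rate, would weaken both conclusions.

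**Working it through.** **1. The plan's own figure.** Inputs from 9.1: n = 176 per arm, difference 3, SD 10, alpha 0.05 (two-sided reproduces the figure).
- Standard error = 10 × √(2/176) = 1.066, so the noncentrality is 3/1.066 = 2.814 on 350 degrees of freedom.
- The noncentral-t power is 80.14%, against 80.04% printed. The figure reproduces.

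**2. The fourfold step, on the days scale.** With N = 1408 and two equal subsets there are 352 patients per arm in each subset.
- Standard error within a subset = 10 × √(2/352) = 0.754.
- Standard error of the between-subset difference = √2 × 0.754 = 1.066.
- For a 3-day between-subset difference, power = Φ(2.814 − 1.960) ≈ 80.4%. Only the difference enters, so the power is the same for 4.5 vs 1.5, 6 vs 3 and 3 vs 0 days.

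The fourfold factor is therefore right for a days-scale interaction test with a 50:50 marker.

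**3. The rule in 9.2.1 under the same conditions.** Simulation with normal outcomes, noninformative prior, SD 10 in both subsets, 50:50 marker, N = 1408 and one look. Assumed thresholds: λ 1 to 2, γ 0.80 to 0.95.

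| True effect in days (subset vs rest) | Ratio rule, range over λ and γ | Days-scale interaction test |
|---|---|---|
| 4.5 vs 1.5 | about 0–84% | about 80% |
| 6 vs 3 | about 3–98% | about 80% |
| 3 vs 0 | about 0–15% | about 80% |

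The top of each range is at λ = 1, γ = 0.80, and the bottom is at λ = 2, γ = 0.95.

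The last row can be understood without simulation. When the true comparator effect is zero, a flat prior makes P(θ₋ > 0 | X) uniform across trials. θ₊ lies 3/0.754 = 4.0 standard errors above zero, so the ratio is positive almost only when θ₋ is positive. The rule can then fire in at most about 1 − γ of trials: 20% at γ = 0.80 and 5% at γ = 0.95.

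**4. Tolerance scaling.** Take the same +10 points of harm in both subsets, with assumed control rates of 10% and 40%.
- Average rates are 15% and 45%, so p̄(1 − p̄) = 0.1275 and 0.2475.
- Ratio of scaled effects = 0.2475/0.1275 = 1.94. With a square-root divisor (a root sign may have been lost in reading the PDF) it is √1.94 = 1.39. On the plain risk difference it is 1.00.
- At N = 1800, λ = 1 and γ = 0.90, the rule fires in about 60% of trials with the printed divisor or 26% with its square root, against about 4% on the risk difference.
- With control rates of 30% and 40%, p̄(1 − p̄) = 0.2275 and 0.2475. The ratio is 1.09, or 1.04 with the root, which is a small effect.

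**5. Days scaling, if the SD is specific to the subset.** With an equal 3-day benefit the ratio is SD₋/SD₊.
- The only printed spreads are by arm: "hydrocortisone+fludrocortisone group was 17.1 ± 10.8 versus 15.0 ± 11.1 in the placebo group". If two subsets differed only that much, the ratio would be 11.1/10.8 = 1.03. At N = 1800, λ = 1.25 and γ = 0.90, the rule would fire in 2.2% of trials against 1.6% on unscaled days.
- With assumed SDs of 8 vs 10, the ratio is 1.25. At N = 1800 the rule fires in about 31% of trials at λ = 1/γ = 0.90, 10% at 1.25/0.90 and 3% at 1.5/0.90.

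**The case against.** **The standard deviation is called common.** If that means common to both subsets, it cancels in the ratio and the days part of the scaling problem disappears. This objection has weight. The definition of the effect size within each subgroup favours an SD common to the two arms inside a subset, but does not settle it. A reader might infer that an equal gain in days will be declared an interaction. The protocol does not support that: it prints no SD by biomarker subset, and the result depends heavily on λ and γ. The tolerance divisor carries the subset index, so that part does not turn on this reading.

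**The 80.04% is attached to a t-test and is correct.** That is so, and the arithmetic is not at fault. But the next sentence carries that power over to interactions, and 9.2.1 judges interactions by the ratio.

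**The rule's power may exceed 80%.** It may, at lenient thresholds when both subsets benefit. A reader might infer that the rule is always weaker than stated. What can be shown is only that its power is not fixed by the 80%.

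**λ, γ and simulated operating characteristics belong in the statistical analysis plan.** Agreed. Section 4.5.2 promises that plan before the first interim analysis, and their absence here is not counted as a fault.

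**The ratio is a published criterion, and the rule only may stop recruitment.** Both are true. Neither transfers a t-test's power to the ratio.

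**Conclusion.** The point holds in two parts.

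**Power.** The 80% in 9.1 describes a days-scale test and not the rule in 9.2.1. For the same 3-day between-subset difference, the rule's power runs from near 0% to about 98% depending on λ, γ and the level of benefit. It stays at or below about 15% when the comparator subset has no benefit.

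**Scaling.** For tolerance, equal absolute harm can give a ratio well away from 1 when background rates differ widely (1.94 or 1.39 for 10% vs 40%), and close to 1 when they do not. For days the same can happen only if the SD is specific to the subset. Its size cannot be judged from the protocol, and it is negligible at the spreads that are printed.

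The figures assume a 50:50 marker, one look, flat priors and, for days, normal outcomes. Vasopressor-free days are bounded and skewed, so the simulated percentages are illustrative. The mismatch between the two sections does not depend on them.

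**What to change.** **Section 9.2.1.** Base the criterion on the posterior distribution of the between-subset difference in treatment effect: mean days for efficacy, risk difference for tolerance. If the ratio is kept, state at least that one SD and one event rate, pooled over both subsets, are the divisors, so that they cancel. Pooling removes the scaling problem but not the instability when the comparator effect is near zero.

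**Section 9.1.** State that the 80% belongs to a days-scale interaction test, or replace it with the simulated power and false-positive rate of the rule actually used.

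**Cost.** Wording in two sections and a short simulation, with no additional patients. The difference form departs from the cited published effect-size criterion. If the ratio is kept, the quoted power may fall.

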9.2.2 Reduction of Bias

Risk of selection bias will be reduced by concealed randomization using variable and undisclosed blocks. Physicians, nurses, patients and family members, all research personnel, and outcome assessors and adjudicators will be blinded. Accordingly, decisions to discontinue life-sustaining therapies and other outcomes that require subjective assessments (e.g. HRQoL) will not be affected by individually held beliefs regarding the effects of corticosteroids.

10 Quality Control and ASSURANCE

Every research project involving human participants managed by AP-HP is ranked according to the projected risk incurred by study participants using the classification system specific to AP-HP sponsored interventional research involving human participants.

10.1 GENERAL ORGANISATION

The sponsor must ensure the safety and respect of individuals who have agreed to participate in the study. The sponsor must implement a quality assurance system to best monitor the implementation of the study in the investigation centres.

For this purpose, the sponsor shall assign Clinical Research Associates (CRA) whose primary role is to carry out regular follow-up visits at the study locations, after having carried out the initial visits. The purpose of monitoring the study, as defined in the Good Clinical Practices (GCP section 5.18.1), is to verify that:

- · the rights, safety and protection of the research participants are met
- the data reported are exact, complete and consistent with the source documents
- the study is carried out in accordance with the protocol in force, the GCPs and the statutory and regulatory provisions in force

10.1.1 Strategy for centre opening

The opening strategy of the centers will be determined before the start of the research.

10.1.2 Scope of centre monitoring

In the case of this risk study (B), the appropriate monitoring level has been determined based on the complexity, the impact and the budget for the study. Therefore, in agreement with the coordinating investigator, the sponsor has determined the logistical score and impact, resulting in a study monitoring level to be implemented: intermediate level.

10.2 QUALITY CONTROL

A Clinical Research Associate (CRA) appointed by the sponsor will be responsible for the good completion of the study, for collecting, documenting, recording and reporting all handwritten data, in accordance with the Standard Operating Procedures applied within the DRCI (Clinical Research and Innovation Department) and in accordance with Good Clinical Practices as well as the statutory and regulatory requirements.

The investigator and the members of the investigator's team agree to make themselves available during regular Quality Control visits carried out by the Clinical Research Associate. During these visits, the following elements will be reviewed depending on the monitoring level:

- written consent
- compliance with the study protocol and with the procedures defined therein
- quality of the data collected in the case report form: accuracy, missing data, consistency of the data with the "source" documents (medical files, appointment books, original copies of laboratory results, etc.)
- management of the treatments used

10.3 CASE REPORT FORMS

All information required by the protocol must be entered in the case report forms. The data must be collected as and when they are obtained, and clearly recorded in these case report forms. Any missing data must be coded.

Every site will have access to the electronic case report forms via a web-based data collection system. Investigators will be given a document offering guidance on using this tool.

When the investigators complete the case report form via the Internet, the CRA can view the data quickly and remotely. The investigator is responsible for the accuracy, quality and relevance of all the data entered. In addition, the data are immediately verified as they are entered, thanks to consistency checks. To this end, the investigator must validate any changes to the values in the case report form. An audit trail will be kept of all changes. A justification can be added when applicable, as a comment.

A print-out, authenticated (signed and dated) by the investigator, will be requested at the end of the study. The investigator must archive a copy of the authenticated document that was issued to the sponsor.

10.4 MANAGEMENT OF NON-COMPLIANCES

Any events that occur as a result of non-compliance – by the investigator or any other individual involved in running the study – with the protocol, standard operating procedures, good clinical practices or statutory and regulatory requirements must be recorded in a declaration of non-compliance and sent to the sponsor.

These non-compliances will be managed in accordance with the sponsor's procedures.

10.5 AUDITS/INSPECTIONS

The investigators agree to consent to the quality assurance audits carried out by the sponsor as well as the inspections carried out by the competent authorities. All data, documents and reports may be subject to regulatory audits and inspections. These audits and inspections cannot be refused on the grounds of medical secrecy.

An audit can be carried out at any time by individuals appointed by the sponsor and independent of those responsible of the research. The aim of the audits is to ensure the quality of the study, the validity of the results and compliance with the legislation and regulations in force.

The persons who manage and monitor the study agree to comply with the sponsor's requirements and with the competent authority regarding study audits or inspections.

The audit may encompass all stages of the study, from the development of the protocol to the publication of the results, including the storage of the data used or produced as part of the study.

10.6 PRINCIPAL INVESTIGATOR'S COMMITMENT TO ASSUME RESPONSIBILITY

Before starting the study, each investigator will give the sponsor's representative a copy of his/her updated personal *curriculum vitæ*, signed and dated less than one year, with his/her RPPS number (*Répertoire Partagé des Professionnels de Santé*, Collective Database of Health Professionals). The CV must include any previous involvement in clinical research and related training.

Each investigator will commit to comply with legislation and to conduct the study in line with GCP, in accordance with the Declaration of Helsinki.

The Principal Investigator at each participating site will sign a commitment of responsibility (standard DRCI document) which will be sent to the sponsor's representative.

The investigators and their staff will sign a delegation of duties form specifying each person's role and will provide their CV.

11 ETHICAL AND LEGAL CONSIDERATIONS

11.1 METHODS FOR INFORMING RESEARCH PARTICIPANT AND OBTAINING THEIR CONSENT

In accordance with Article L1122-1-1 of the Code de la Santé Publique (French Public Health Code), no interventional research involving human participants can be carried out on a person without his/her freely given and informed consent, obtained in writing after the person has been given the information specified in Article L.1122-1 of the aforementioned Code.

All consecutive eligible patients should be approached for participation in the trial by the clinical investigators or person qualified to carry out the research. The clinical investigator will inform the eligible person then collect the free and written consent of the person undergoing to the research. If the patient is unable to provide consent within the time window allowed by the protocol, his or her authorized person (member family, curator, guardianship, trusted person) may be approached in person. The local research team could also enroll eligible patients and obtain consent subsequently as per French national regulation under a deferred consent model.

To obtain informed consent, study personnel should follow the following steps:

- Present information on the study in a simple and understandable manner;
- Answer questions in a simple and understandable manner;
- Allow the potential participant/authorized persons an opportunity to reflect and discuss study participation with their family, friends, or family physician if desired;
- Confirm that the participant/authorized persons understands the risks and benefits of participating in the study and that their participation is voluntary;
- Complete and obtain signatures for informed consent form and obtain contact information from the participant/authorized persons.

A copy of the information note and consent form, signed and dated by the research participant / legal representative and by the principal investigator or the physician representing the investigator will be given to the individual / legal representative prior to their participation in the study. The principal investigator or the physician representing him/her will keep a copy.

At the end of the study, one copy will be placed in a tamper-proof sealed envelope containing all the consent forms. This envelope will be archived by the sponsor.

In addition, the investigator will specify in the person's medical file the person's participation in the research, the procedures for obtaining his/her consent or consent from his or her authorized person as well as the methods used for providing information for the purpose of collecting it. The investigator will retain one copy of the signed and dated consent form.

